7.3 Subject Population(s) for Analysis

The study participants whose data will be subjected to data analysis include:

- All-treated population: Any subject entered into the study that received at least one dose of study drug.
- All-completed population: Only subjects who completed all study related procedures and follow-up will be included

8 Safety and Adverse Events

8.1 Adverse events and study discontinuation

Patients will be discontinued from the study if they: 1) request withdrawal from the study, 2) develop worsening of underlying liver function defined as doubling of serum total bilirubin and/or increase in ALK or AST to $\geq 3x$ the upper limit of normal or baseline levels without mechanical biliary obstruction, 3) have side effects to study drug (e.g. diarrhea) that are not controlled by over the counter medication (e.g. loperamide), or 4) experience an adverse event based on CTCAE 4.0 criteria of grade 3 or higher that is not related to underlying disease.

When an adverse event has been identified, the study team will take appropriated action necessary to protect the study participant and then complete the Study Adverse Event Worksheet and log. The investigators will evaluate the event and determine the necessary follow-up and reporting required (see next section).

8.1.1 Investigator reporting

The investigators will personally supervise the study. An adverse event is defined as any unfavorable and unintended diagnosis, symptom, or disease temporarily associated with use of the study medication, whether or not related to the medication. Worsening of the pre-existing clinical condition will be considered an adverse event and, possibly, treatment failure.

The investigators will use the following definitions to assess the relationship of the adverse event to the use of study drug:

1. Probably related: Adverse event has a strong temporal relationship to study drug or recurs on re-challenge and another etiology is unlikely or significantly less likely.
2. Possibly related: Adverse event has a strong temporal relationship to the study drug and an alternative etiology is equally or less likely compared to the potential relationship to study drug.
3. Probably not related: Adverse event has little or no temporal relationship to the study drug and/or a more likely alternative etiology exists.
4. Not related: Adverse event is due to an underlying or concurrent illness or effect of another drug and is not related to the study drug (e.g., has no temporal relationship to study drug or has a much more likely alternative etiology).

Adverse events will be classified according to severity into: mild (transient and easily tolerated by the participant), moderate (causes the participant discomfort and interrupts the

participant's usual activities), or severe (causes considerable interference with the participant's usual activities and may be incapacitating or life-threatening). A serious adverse event is defined as any untoward medical occurrence that results in death, is life-threatening, requires or prolongs hospitalization, causes persistent or significant disability/incapacity, or, in the opinion of the investigators, represents other significant hazards or potentially serious harm to research participants.

The investigators will be responsible for communicating adverse events to the Mayo Institutional Review Board (IRB), the Data and Safety Monitoring Board, Co-investigators, and the Food and Drug Administration. The following information will be recorded in the study database and provided as indicated:

- Medical record number:
- Disease/histology (if applicable):
- The date the adverse event occurred:
- Description of the adverse event:
- Relationship of the adverse event to the research (drug, procedure, or intervention):
- If the adverse event was expected:
- The severity of the adverse event: (use a table to define severity scale 1-5)
- If any intervention was necessary:
- Resolution: (was the incident resolved spontaneously, or after discontinuing treatment)
- Date of Resolution:

8.1.2 Investigator reporting: Notifying the FDA

The investigators will report to the FDA all unexpected, serious suspected adverse reactions according to the required IND Safety Reporting timelines, formats and requirements.

Unexpected fatal or life threatening suspected adverse reactions where there is evidence to suggest a causal relationship between the study drug/placebo and the adverse event, will be reported as a serious suspected adverse reaction. This will be reported to the FDA on FDA Form 3500A, no later than 7 calendar days after the investigator's initial receipt of the information about the event.

Other unexpected serious suspected adverse reactions where there is evidence to suggest a causal relationship between the study drug/placebo and the adverse event, will be reported as a serious suspected adverse reaction. This will be reported to the FDA on FDA Form 3500A, no later than 15 calendar days after the investigator's initial receipt of the information about the event.

Any clinically important increase in the rate of serious suspected adverse reactions over those listed in the protocol or product insert will be reported as a serious suspected adverse reaction. This will be reported to the FDA on FDA Form 3500A no later than 15 calendar days after the investigator's initial receipt of the information about the event.

Findings from other studies in human or animals that suggest a significant risk in humans exposed to the drug will be reported. This will be reported to the FDA on FDA Form 3500A, no later than 15 calendar days after the investigators initial receipt of the information about the event.

8.2 Stopping Rules

The study will be stopped if two or more participants develop an adverse event based on Common Terminology Criteria for Adverse Events (CTCAE) 4.0 criteria of grade 3 or higher OR if one patient develops an adverse event based on CTCAE 4.0 criteria of grade 4 or higher that is not related to the participant's underlying disease.

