4.4.1 When and How to Withdraw Subjects

Participants will be withdrawn from the study if they experience a CTCAE 4.0 criteria grade 3 or higher adverse event, are unable to adhere to the study protocol, inadvertently become pregnant during the study (in which case they will be referred to their primary physician for obstetric care), or experience treatment failure as described in section 3.4 above.

Participants may voluntary withdraw from the study for any reason. Patients who withdraw from the study (or decline participation) will not be penalized in any way. Specifically, they do not have to be in this study to receive or continue to receive medical care from Mayo Clinic.

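### Sections 4.4.1, 8.1 and 8.2 conflict on whether disease-related grade 3 or higher events count towards withdrawal and the study stop

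*Combined protocol and SAP*

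**What the plan says.** Three sections set rules for CTCAE 4.0 events of grade 3 or higher.

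- **Section 4.4.1 (withdrawal):** "Participants will be withdrawn from the study if they experience a CTCAE 4.0 criteria grade 3 or higher adverse event". There is no condition about cause.
- **Section 8.1, item 4 (discontinuation):** patients are taken off study if they "experience an adverse event based on CTCAE 4.0 criteria of grade 3 or higher that is not related to underlying disease".
- **Section 8.2 (study stop):** the first limb begins "The study will be stopped if two or more participants develop an adverse event" and sets the level at grade 3 or higher. The second limb reads "OR if one patient develops an adverse event based on CTCAE 4.0 criteria of grade 4 or higher that is not related", and the sentence closes by naming the patient's underlying disease.

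Section 8.1.1 makes disease progression reportable: "Worsening of the pre-existing clinical condition will be considered an adverse event and, possibly, treatment failure". The same section describes severity in two ways. One is a three-class scale whose top class is "severe (causes considerable interference with the participant's usual activities and may be incapacitating or life-threatening". The other is a field in the list of recorded items, with the prompt "use a table to define severity scale 1-5" and no table supplied.

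**The concern.** The qualifier that sets aside disease-related events is absent in 4.4.1, present in 8.1 and ambiguous in 8.2. A patient with a grade 3 event caused by the liver disease meets the withdrawal rule in 4.4.1 but not item 4 of 8.1. Two such patients either stop the study or do not, depending on how one sentence in 8.2 is parsed.

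Section 8.2 is the only study-level stopping rule in the documents. If its meaning is settled only after events occur, in an open-label study, it will be settled by people who know which events are in question and what each reading would do. A stopping rule is meant to prevent that.

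**Working it through.** **Step 1. The rules side by side, for disease-related events only**

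| Situation | 4.4.1 | 8.1 item 4 | 8.2, reading A | 8.2, reading B |
|---|---|---|---|---|
| One patient, grade 3 | withdrawn | not triggered | no stop | no stop |
| One patient, grade 4 or higher | withdrawn | not triggered | no stop | no stop |
| Two patients, grade 3 or higher | both withdrawn | not triggered | study stops | no stop |

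Reading A applies the qualifier to the grade 4 limb only. Reading B applies it to both limbs. The grammar allows either.

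**Step 2. Inputs for the size of the gap**

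- n = 15 patients (sections 3.1, 4.3 and 7.1; the header of Table 1 says 20).
- p = the proportion of patients with at least one disease-related grade 3 or higher event during the study. The documents give no value, so 2%, 5%, 10% and 15% are assumed.
- Patients are taken as independent. At first, no other grade 3 or higher events are assumed.

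The documents state no stopping probability, so there is no figure of theirs to reproduce.

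**Step 3. Chance of a stop**

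Reading A: P(stop) = 1 − (1 − p)^15 − 15p(1 − p)^14. Reading B: P(stop) = 0, because no event counts.

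| Assumed p | (1 − p)^15 | 15p(1 − p)^14 | P(stop), A | P(stop), B |
|---|---|---|---|---|
| 2% | 0.739 | 0.226 | 3.5% | 0% |
| 5% | 0.463 | 0.366 | 17% | 0% |
| 10% | 0.206 | 0.343 | 45% | 0% |
| 15% | 0.087 | 0.231 | 68% | 0% |

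**Step 4. Does the gap survive if other events also occur?**

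Suppose a further 5% of patients have a grade 3 or higher event not due to the disease, one fifth of these being grade 4 or higher (4% grade 3, 1% grade 4 or higher). Each patient is placed in one category. With q = 1 − p − 0.05:

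- Reading A: P(stop) = 1 − q^15 − 15(p + 0.04)q^14. This gives 48.5%, 69.7% and 83.9% at p = 5%, 10% and 15%.
- Reading B: P(stop) = 1 − 0.95^15 − 15(0.04)(0.95^14) = 1 − 0.463 − 0.293 = 24.4% at every p.

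The readings still differ by 24 to 60 percentage points.

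**Step 5. Withdrawals**

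The expected number withdrawn for disease-related events under 4.4.1 is 15p: 0.3, 0.75, 1.5 and 2.25 patients at the four assumed rates. Under item 4 of 8.1 it is 0. These differences are upper limits, because other criteria would remove some of the same patients under either section.

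**The case against.** Several points weigh against the concern.

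- **The two withdrawal lists could be read together.** A patient who meets either list leaves the study. That is workable, but item 4 of 8.1 would then have no effect of its own, since 4.4.1 already covers every grade 3 or higher event. The documents do not say which section governs, and this reading does not settle 8.2.
- **The affected group is smaller than it looks.** Section 4.2 excludes decompensated cirrhosis, recent untreated dominant stricture, recent suspected cholangitis, uncontrolled bowel disease, known or suspected cholangiocarcinoma and an anticipated need for transplant within a year. Biochemical deterioration without mechanical obstruction leads to withdrawal under both 4.4.1 (through 3.4) and 8.1. Section 4.4 also lets investigators withdraw a patient in that patient's interest. All of this stands. It narrows the conflict on withdrawal to the remaining disease-related events, and none of it says what 8.2 counts.
- **The rates are assumed.** This also stands. The calculation shows that the wording can matter, not how often it will.

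A reader might also infer two stronger points that the documents do not support.

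- **That withdrawal for an adverse event adds to the failures in the primary analysis.** The failure list in 3.4 names biochemical deterioration, voluntary discontinuation, death and transplantation. It does not name withdrawal required by the adverse event rule. Section 3.2 defines success by alkaline phosphatase alone, and section 6 has that test drawn at week 12 or early termination. How these withdrawals enter the analysis is not stated.
- **That the severity scale loses the grades on which 8.2 depends.** The three-class scale does place life-threatening events with other severe ones. But 4.4.1, 8.1 and 8.2 each refer to CTCAE 4.0 directly, and 8.1.1 also asks for a 1 to 5 severity. The grades are therefore not shown to be lost.

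**Conclusion.** The conflict is real and can be seen from the text alone: the disease qualifier is missing in 4.4.1, stated in 8.1 and of unclear reach in 8.2. Because 8.1.1 treats worsening of the existing condition as an adverse event, the events concerned can occur.

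Under the assumptions in steps 2 and 3, the chance of a study stop ranges from 3.5% to 68% on one reading of 8.2 and is 0% on the other. The range rests on rates that the documents do not provide. It does not show that disease-related events of this grade are to be expected in this selected population over 12 weeks, or that a stop is likely.

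The severity scales are a side issue. Two coexist in 8.1.1, the table for one is missing, and neither is tied to CTCAE.

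**What to change.** The sponsor should reconcile 4.4.1, 8.1 and 8.2. Each should say whether events related to the underlying disease count, and 8.2 should say whether the qualifier covers one limb or both. Writing the two limbs of 8.2 as separate sentences, each with its own statement on disease-related events, would remove the ambiguity. Which rule applies is for the sponsor to decide.

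As a side note, section 8.1.1 should define its 1 to 5 severity field as the CTCAE 4.0 grade, so that the rules can be applied from the recorded data. The mild, moderate and severe classes need not be removed for this. If the disease qualifier is kept in any rule, the adverse event form should also record whether the event was judged related to the underlying disease. At present 8.1.1 defines relatedness to study drug only, with underlying illness as one of several grounds for its lowest category.

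The cost is protocol and case report form wording. No extra patients, visits or tests are needed.

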8.3 Medical Monitoring

It is the responsibility of the principle investigators to oversee the safety of the study at their site. This safety monitoring will include careful assessment and appropriate reporting of adverse events as noted above, as well as the construction and implementation of a site data and safety-monitoring plan (see section 10 “Study Monitoring, Auditing, and Inspecting”). Medical monitoring will include a regular assessment of the number and type of serious adverse events.

9 Data Handling and Record Keeping

9.1 Confidentiality

Information about study subjects will be kept confidential and managed according to the requirements of the Health Insurance Portability and Accountability Act of 1996 (HIPAA). Confidentiality of patient information will be protected by using a study number to identify participants. Data collection forms will be kept in locked files designated for this study within an office, and computerized data will be password-secured.

9.2 Records Retention

The investigators will maintain records and essential documents related to the conduct of the study. These will include subject case histories and regulatory documents.

The investigators will retain the specified records and reports for;

1. Up to 2 years after the marketing application is approved for the drug; or, if a marketing application is not submitted or approved for the drug, until 2 years after shipment and delivery of the drug for investigational use is discontinued and the FDA has been so notified or
2. As outlined in the Mayo Clinic Research Policy Manual –“Access to and Retention of Research Data Policy” http://mayocontent.mayo.edu/research-policy/MSS_669717 , whichever is longer

10 Study Monitoring, Auditing, and Inspecting

10.1 Study Monitoring Plan

The investigator will allocate adequate time for such monitoring activities. The Investigator will also ensure that the monitor or other compliance or quality assurance reviewer is given access to all the study-related documents and study related facilities (e.g. pharmacy, diagnostic laboratory, etc.), and has adequate space to conduct the monitoring visit.

This study will be monitored on a routine basis during the conduct of the trial. The Mayo Clinic Office of Research Regulatory Support will be allowed to provide clinical monitoring for the trial as a service for the sponsor-investigator. Clinical trial monitoring requires review of the study data generated throughout the duration of the study to ensure the validity and integrity of the data along with the protection of human research subjects. This will assist sponsor-investigators in complying with Food and Drug Administration regulations.

10.2 Auditing and Inspecting

The investigator will permit study-related monitoring, audits, and inspections by the IRB, the sponsor, and government regulatory agencies, of all study related documents (e.g. source documents, regulatory documents, data collection instruments, study data etc.). The investigator will ensure the capability for inspections of applicable study-related facilities (e.g. pharmacy, diagnostic laboratory, etc.).

Participation as an investigator in this study implies acceptance of potential inspection by government regulatory authorities and applicable compliance offices.

11 Ethical Considerations

This study is to be conducted according to United States government regulations and Institutional research policies and procedures.

This protocol and any amendments will be submitted to a properly constituted local Institutional Review Board (IRB), in agreement with local legal prescriptions, for formal approval of the study. The decision of the IRB concerning the conduct of the study will be made in writing to the sponsor-investigator before commencement of this study.

All subjects for this study will be provided a consent form describing this study and providing sufficient information for subjects to make an informed decision about their participation in this study. This consent form will be submitted with the protocol for review and approval by the IRB for the study. The formal consent of a subject, using the Approved IRB consent form, must be obtained before that subject undergoes any study procedure. The consent form must be signed by the subject or the subject's legally authorized representative, and the individual obtaining the informed consent.

12 Study Finances

12.1 Funding Source

This study will be funded by Europharma.

